9.3. Subject Consent

If the subject is deemed eligible after BQE and medical record reviewing, the research team member may then approach the potential subject to discuss participation in the study, including background of the proposed study, inclusion and exclusion criteria, the benefits and risks of the procedures and the follow-up requirements. If the study is of interest to the subject, the informed consent form (ICF) will be discussed and presented. The subject must sign the ICF prior to enrollment. This form must have prior approval of institutional review board (IRB)/ ethics committee (EC) for all participating sites. Failure to obtain informed consent will render the subject ineligible for the study.

Patients will be approached to obtain written informed consent prior to any study specific procedures being performed. The purpose of the study and the benefits and risks of the procedures will be explained to the subject in their local language. The consent process must be documented accordingly in the medical record. Patients who agree to study participation must sign an IRB/EC-approved ICF. Subjects will be informed that their participation in this study is voluntary and they may refuse to participate or discontinue from the study at any time. Subjects will be given the opportunity to ask the investigator questions so that they are adequately informed about the research. A copy of the signed informed consent must be provided to the subject and the informed consent process will be documented in source documents.

If new information becomes available that may affect a subject's decision to continue to take part in the study, this information will be discussed with the subject by the investigator.

Subjects will be assured that they may withdraw from the study at any time for any reason.

9.4. Treatment Assignment

9.4.1. Treatment Phase

Patient History

After the subject signs the ICF, the **Patient History CRF** is completed for that subject.

Baseline Qualifying Tests

Results from the subject's BQE including pathology review and baseline staging tests (EUS and/or CT where applicable) are entered onto the **Baseline Qualifying CRF**. Afterwards, definitive eligibility will be assessed by completing the **Eligibility CRF**.

Primary Radiofrequency Ablation

If the subject is found to be eligible for the study after BQE, central review of the BQE pathology results and reviewing medical records, he or she will proceed to the primary ablation session within 1 week - 3 months after BQE. Primary RFA will be observed by an expert from CICAMS.

1. Start WLE to document landmarks and to check all selection criteria that can be assessed endoscopically (e.g. appearance of the lesion, confirmed absence of non-flat lesions, strictures, presence of varices, eosinophilic esophagitis, reflux esophagitis, etc.)
2. Lugol's staining and assessment of all endoscopic selection criteria
3. Assessment of definitive eligibility of the subject.
4. Marking on the estimated TA with electrocoagulation (preference is not to use APC for this).
5. Measuring will be performed. If the inner diameter of the esophagus is less than 18mm, the patient is ineligible for the study.
6. Primary RFA is performed with the Barrx™ Circumferential Radiofrequency Ablation System. The ablation zone must encompass the entire TA. The energy density setting is 12 J/cm², applied once, using the default power set by the RF generator according to catheter size, with no cleaning of coagulum.
7. Beginning proximally, the electrode is deployed so that the proximal margin of the electrode is aligned with the proximal marker. The balloon is automatically inflated and ablation energy is delivered.
8. After automated deflation of the balloon, air is insufflated by the endoscope and the catheter carefully advanced distally avoiding denuding of the ablated mucosa. The proximal margin of the electrode is aligned with the distal margin of the first ablation zone minimizing overlap between zones. Ablation is performed.
9. These steps are repeated until the ablation overlaps the distal markings.
10. Tattoos are placed in at least 2 quadrants at the most proximal and distal extent of TA (providing at least 1 cm margin between proximal tattoo and most proximal USL, and at least 1 cm margin between distal tattoo and most distal USL).

All data from the RFA procedure are entered onto the **Endoscopy CRF**.

3, 6, 9 months (from primary RFA, +/- 4 weeks) Follow-up Endoscopy, Biopsy, and Additional RFA

After baseline treatment, patient will return for standardized endoscopies at 3, 6 and 9 months, (from primary RFA, +/- 4 weeks), to endoscopically assess the TA for USLs using Lugol's iodine. All endoscopies in the treatment phase will be observed by an expert from CICAMS. The following two treatment scenarios are possible based on the presence or absence of USLs. For every endoscopy, the **Endoscopy CRF**, the **Table of findings CRF** and the **Pathology CRF** will be completed.

Scenario #1: No USLs are present

At the 3 months FU visit, (from primary RFA, +/- 4 weeks), biopsy sampling of TA will be performed to confirm absence of occult MGIN or worse: Using a maximum capacity forceps or larger (for example, Boston Scientific Radial Jaw 3 or 4) and commencing at the most proximal extent of the original USL-bearing portion of the esophagus and tattoos as reference points, 2 biopsy specimens are obtained for every 2 cm segment of the original USL-bearing esophageal segment. The most distal biopsies are obtained 1 cm above the distal Tattoo. All fragments from a particular 2 cm level are placed in the same pathology specimen container and labeled as to their location (cm from the incisors). In this manner, the portion of the esophagus that originally contained USLs is well-sampled (tissue at baseline that was both USL and non-USL), with the allowance of focusing some biopsies at each level in certain areas based on original USL location (referring to baseline imaging and CRF's). Re-tattoos will be performed if necessary.

*Example: Baseline USL-bearing portion of the esophagus is 30-36 cm (therefore, TA 29-37 cm). A total of 6 biopsies would be obtained (approximately two fragments each at 30-32, 32-34, and 34-36). Biopsies of the 1 cm "safety zone" at either end of TA are **not** obtained in any biopsy session.*

At the 6 and 9 months FU visit, (from primary RFA, +/- 4 weeks), no biopsies will be performed from normally stained TA.

No RFA is applied in "Scenario #1: no USLs are present."

In the very unlikely scenario that any biopsy subsequently shows MGIN+ despite a normally stained esophagus, the entire TA is treated once again with circumferential or focal RFA (to ensure complete treatment of any occult neoplasia.)

Scenario #2: USLs are present in the TA

If there are **residual flat USLs within the original TA**, the investigator records the extent of the USLs (length, diameter, location) and obtains biopsies of each USL starting distally and moving proximally as follows:

For each two centimeters in length, 1 level of biopsies will be performed. The number of biopsies per level depends on the circumferential extent of the USL as follows:

- <25% of circumference: 1 biopsy per level
- 25 – 49% of circumference: 2 biopsies per level
- 50 – 74% of circumference: 3 biopsies per level
- ≥75% of circumference: 4 biopsies per level.

Example: for a USL of 3 centimeter in length covering 60% of circumference, 2 levels with 3 biopsies per level will be performed, summing up to a total of 6 biopsies.

Each set of unique USL samples are placed in individual containers, and labeled as to their location. If 3 or more biopsies are obtained from a single USL, use multiple jars for that USL with a maximum of 2 biopsies per jar. The investigator designates the staining characteristic of each tissue area prior to biopsy, and enters this information on the Table of findings CRF. It is presumed that biopsies from USLs are unstained, while biopsies from the non-USL TA are "stained". The CRF also contains information about each specimen/USL location.

Treatment of USL

In general, all residual flat USLs during follow-up will be treated with RFA.

USLs that are deemed clearly reactive can be biopsied without need for additional treatment. Clearly reactive USLs will be defined as any USL with stain code III (lightly stained) that is deemed as non-suspicious for ESCN and reactive after RFA on both WLE and NBI by the Investigator. If a USL will be deemed reactive and therefore left untreated, and if subsequent biopsies do show MGIN or worse, the USL will then be treated on the next endoscopy, independent of the endoscopic appearance.

If subsequent biopsies show cancer, patients is defined as progressor will be considered a failure for the primary endpoint and he will be offered escape treatment (see section 9.4.3. for description), at the discretion of the physician under the hospital standard of care.

If an indication for additional RFA exists, the investigator will determine whether to provide secondary RFA with the circumferential or focal device, based on the extent of disease:

- If lesions involve more than 3/4 of the circumference, circumferential RFA will be used
- If lesions involve less than 3/4 of the circumference, focal RFA will be used
 - It is presumed that all secondary RFA procedures will be performed with the focal device, and this presumption is reflected in Figure 1.

If focal RFA is selected, it is important to note that the effect of Lugol's may significantly wane during the biopsy procedures therefore it may be necessary to reapply the Lugol's in order to target the remaining USLs. Or simply use the biopsy sites for targeting. Each USL is treated so that the ablation effect overlaps at least 5 mm onto the normal staining esophageal mucosa surrounding the USL. The energy density setting is 12 J/cm² and the power density setting is 40 W/cm². Each USL is ablated 3x without changing the position of the catheter. Upon completing focal RFA of USL(s), biopsies are obtained from the TA avoiding all acute RFA sites. Two biopsy fragments are obtained from every 2 cm of the original USL-bearing esophagus that was not treated at this session (see Figure 1).

Example: TA from 30-40, USL bearing esophagus 31-39. One USL at 3 months from 31-32. Sample USL, then RFA USL. Then obtain 2 biopsy fragments from every 2 cm starting at 33-35, 35-37, and 37-39 cm. The area of the USL is avoided (31-33 cm).

In the unlikely event that circumferential RFA is selected for a follow-up RFA, the entire extent of original TA is treated, using same technique as at the primary RFA session.

If necessary, a maximum of four RFA sessions will be performed in total for each patient in this study. If USLs with MGIN or worse in the TA persist after four sessions, the subject is considered a failure for the primary endpoint. Such patients will undergo escape treatment.

Scenario #3: Lesions Suspicious for ESCC Are Present in the TA

If any **non-flat USL (Paris type 0-I, 0-IIa, 0-IIc, 0-III)** is detected, independent of its staining characteristics upon Lugol's staining, or WLE, NBI or Lugol's chromoendoscopy show a lesion suspicious for ESCC (e.g. 'pink sign' USL, defined as a color change after Lugol's staining: initially whitish yellow and pink 2-3 minutes later), or if previous biopsies from this lesion showed ESCC, subject will be managed with escape treatment (see section 9.4.3 for description), at the discretion of the physician under hospital standard of care depending on the lesion type. If histology is needed before

escape treatment, a keyhole biopsy should be performed, but the Investigator can perform escape treatment if deemed necessary, regardless of the biopsy result. The patient will be considered a failure for the primary efficacy endpoint only if escape treatment histology shows progression to ESCC. If histology does not show ESCC, the patient will return in 3 months from escape treatment for possible RFA and will be eligible for success in the primary endpoint. For continuation on trial, please refer to section 9.4.3.

Scenario #4: USLs are present outside the TA

If any **new USL(s) is (are) detected outside the TA** during follow-up prior to 12 months, it is biopsied and the biopsy fragments are placed in a separate container and labeled as to their location. This finding does not alter the plan for RFA inside TA for that particular procedure, and the USL outside the TA is treated according the standard practice under hospital standard of care.

During all endoscopies, re-tattoos will be performed if necessary. If clinically indicated, extra endoscopies can always be performed.

12 Months Follow-up Endoscopy

No RFA is provided to any subject at the 12-month primary endpoint biopsy visit.

For the biopsy methodology for the primary endpoint:

1. If there are no USLs within the TA, see Section 10.4, "Scenario #1: No USLs are present"
2. If there are one or more persistent USLs within the TA, see Section 10.4, "Scenario #2: USLs are present"

If there are any USLs discovered outside the original USL bearing esophagus, these may be biopsied or resected, but must be submitted in separate containers are not considered in the primary endpoint analysis.

Patients with a CR at 12 months will enter the follow-up phase as described in figure 2 and section 9.4.2.

Patients with residual ESCN at 12 months will be defined as treatment failures, and will undergo escape treatment within 3 months (+/- 4 weeks). If CR will be re-established after escape treatment, patients will stay in the trial and will be followed-up and treated if necessary, according to figure 2. If non-endoscopic treatment is performed at 12 months, or if pathology indicates non-endoscopic treatment, patients won't be treated and/or followed-up according to the study protocol, but will still be followed-up until 5 years after baseline to assess secondary endpoints.

[figure not shown]

Figure 1. Decision Tree for Subject Flow Through in Treatment Phase (adapted from He et al., 2014 (18))

[figure not shown]

Figure 2. Decision Tree for Subject Flow in Follow-Up Phase (adapted from He et al., 2014 (18))

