6.2. Rationale

This study design is a prospective, multi-center, non-blinded, single-arm (non-randomized), post-market study. This study design was selected given the desire to evaluate treatment efficacy (RFA) on a disease state (ESCN) with generally well understood natural history. Two recently published reports have evaluated the Barrx™ Flex Radiofrequency Ablation System for the eradication of ESCN (11, 18). Bergman et al. 2011 reported on 29 subjects (18 MGIN, 10 HGIN, and 1 ESCC) treated with circumferential RFA followed by focal RFA every 3 months until the complete histological eradication of MGIN or worse. Two energy applications were administered at 10 J/cm² or 12 J/cm², with and without cleaning of the coagulum between passes. The primary endpoint was complete response at 12 months, defined as the histological absence of MGIN, HGIN, or ESCC. The rate of complete response was 86% at 3 months after the primary RFA session and 97% at 12 months after the primary RFA session (11). Four strictures (14%) were reported, all dilated to resolution. The authors concluded that RFA was associated with a high rate of histological complete response for the eradication of ESCN with no neoplastic progression (11). Because the stricture rate was slightly higher than typically reported in studies assessing RFA for the treatment of Barrett's Esophagus, the authors concluded that technique and dose may contribute to stricture formation and proposed further evaluation of dosimetry to preserve the high rate of complete response while reducing the stricture rate (11).

The authors continued the study to a total enrollment of 96 subjects (45 MGIN, 42 HGIN, and 9 ESCC). In that analysis, the complete response rate was 73% after 3 months (1 RFA session) and 84% after 12 months. The stricture rate was 21%. However, when using a circumferential RFA dose of 12J/cm² with one application and no cleaning of the coagulum, the stricture rate was only 6%, with complete response rates of 65% and 82% at 3 months and 12 months respectively. This regimen had additional benefit of procedural simplicity. However, only a total of 17 patients were treated with this regimen (18).

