Although preliminary, results for the long-term follow-up of this study will be shortly discussed. Sustained CR during 5 years follow-up was observed in 86% (67/78 patients). Recurrence occurred in 9% (7/78 patients, MGIN 5, HGIN 1). 5 were managed with RFA, one with ESD. Progression of baseline disease occurred in another 5% (4/78 patients; HGIN (n=1), sm-ESCC (n=3)); all were treated with ESD. Two progressor lesions were normally stained after Lugol's and with repeatedly negative biopsies, and were therefore left untreated. Later both lesions were considered suspicious for cancer and escape treatment was performed, with pathology assessment for one case showed submucosal cancer buried under normal epithelial cells. Pathology assessment for the second case is pending.

However, protocol violations during follow-up occurred in the majority of patients (59%) resulting in prolonged follow-up intervals, lesions left untreated or no adequate follow-up after detection of recurrent or progressive disease. This might have interfered with the results, and those might have been better with strict follow-up protocols.

The 12 patients with residual ESCN suffered a poorer prognosis. Fifty-eight percent (7/12 patients) developed progressive disease and were treated with either ESD (n=2) or non-endoscopic treatment (n=5), suggesting that RFA failures should directly be managed with an alternative treatment like EMR or ESD.

Therefore, to further assess the safety, effectiveness, and durability of the Barrx™ Flex Radiofrequency Ablation System for the eradication of ESCN, the current study will employ methods similar to the 2 studies reported above but with a consistent primary RFA dose of 12 J/cm² with one application and no cleaning of the coagulum, and with subsequent 5-years follow-up according to strict study protocols.

7. Product Description

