- Central pathology review of biopsies for all biopsies or resection specimens during FU, with independent reading from two pathologists in case of recurrent or progressive disease.
 - Safety assessment

If clinically indicated, Investigator may always perform extra endoscopies in addition to figure 2.

9.4.3. Escape treatment: Endoscopic (EMR or ESD) or Non-Endoscopic Therapy during Treatment or Follow-up Phase

Several indications for escape treatment exist:

[figure not shown]
- Any non-flat lesion (Paris type 0-I, 0-IIa, 0-IIc, 0-III) during treatment or follow-up phase
- Any abnormality under WLE or Lugol's chromoendoscopy that is suspicious for ESCC (e.g. 'pink sign' USL, defined as a color change after Lugol's staining: initially whitish yellow and pink 2-3 minutes later)
- ESCC in biopsies during treatment or follow-up phase (defined as progression of disease)
- Presence of MGIN or worse in any biopsies from TA at the 12 months endoscopy
- Persistent MGIN or worse during follow-up phase despite a maximum of 4 consecutive 3-monthly RFA sessions
- If clinically indicated per Investigator's discretion

Escape treatment can be performed endoscopically (EMR or ESD), or non-endoscopically (surgery, radiotherapy or chemotherapy) per investigator's discretion under the hospital's standards of care. All patients, regardless of treatment used or failure of the primary endpoint, will be followed to study termination for assessment of secondary endpoints:

- Patients who undergo non-endoscopic therapy will be considered a failure for the primary endpoint, but will be tracked through the 5-year follow-up to assess secondary endpoints.
- For patients who undergo endoscopic treatment, final pathology is required:
 - If the disease stage is eligible for endoscopic escape treatment (i.e.: good to moderate differentiation and negative vertical resection margins and m1/m2/m3/sm1 disease and without lymphovascular infiltration), further treatment and/or follow-up endoscopies after the escape treatment will occur according to

Medtronic Confidential

- the study protocol. The application of RFA after endoscopic resection may be performed after minimally 8 weeks later.

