- If the disease stage exceeds the limits for endoscopic treatment (i.e.: either one of: poor differentiation, positive vertical resection margins, sm-2 or sm-3 invasion or lymphovascular invasion), patient will be considered a failure for the primary endpoint. The Investigator will decide which escape treatment to perform, and the patient will be followed to study termination for assessment of secondary endpoints.
 - If histology does not demonstrate ESCC, patient will remain eligible for inclusion as a success in the primary and secondary endpoints. The application of RFA after endoscopic resection may be performed after minimally 8 weeks later.

Discharge Instructions after RFA Procedures

- Liquid acetaminophen with narcotic per oral as needed for pain
- Liquid antacid, lidocaine, and sucralfate slurry or Almagate Suspension for first 5 days, as needed
- Liquid diet for 3 days, then soft diet for 4 days, then normalize
- At the direction of the physician, anti-thrombotic agents should be avoided for 7 days before and after any RFA procedure.
- All patients commence proton pump inhibitor (PPI) medication (esomeprazole 40 mg bid) after the Primary RFA to allow restoration of a normal epithelium. Patients will continue PPI after each RFA session until endoscopy and biopsy demonstrate no further MGIN+ and no need for further RFA.
- Contact physician for any vomiting, shortness of breath, pain not controlled on medication, fever, or bleeding.
- Subject is educated to not eat very hot foods including soups, and not drink very hot liquids as such behavior can delay healing and potentially promote stricture formation and prolonged pain. Subject is instructed to not eat or drink anything in which they are unable to comfortably place their finger for at least 10 seconds prior to ingesting.

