9.10. Definitions

-CR = complete response

Absence of MGIN or worse in biopsies from TA at a single endoscopy.

- Escape treatment

Escape treatment is indicated for lesions with (i) ESCC in biopsies, (ii) non-flat lesions, or (iii) lesions otherwise suspicious for ESCC (e.g. pink-sign positive lesions). Escape treatment will be performed by investigator's distinction and per hospital's standards of care. Subsequent pathology assessment determines whether patient is defined as progressor and failure for the efficacy endpoint.

- Progressive disease

This term is applicable during the whole study. Progressive disease is defined as ESCC in any biopsy or resection specimen. Progressive disease on biopsy will always be treated with escape treatment.

Patients with progressive disease within the first 12 months are a failure for the primary efficacy endpoint, whereas progression patients in subsequent 4 years of follow-up are a failure for the durability endpoint. Progressive disease can be classified into 2 categories based on pathology:

- Eligible for endoscopic treatment, if all of the following characteristics are met: good to moderate differentiation, negative vertical resection margins, m1/m2/m3/sm1 disease and without lymphovascular infiltration.
- Exceeding the limits for endoscopic treatment, if any of the following characteristics was found: poor differentiation, positive vertical resection margins, sm-2 or sm-3 invasion or lymphovascular invasion.

- Treatment failure

This term is applicable to the first 12 months of study. All patients with residual ESCN at the 12 months endoscopy, and patients who progressed to ESCC before 12 months, will be defined as treatment failures.

- Sustained CR

This term is applicable during follow-up, to all patients that were not defined as treatment failures at 12 months. Sustained CR is defined as sustained eradication of MGIN or worse in biopsies from TA, during all FU endoscopies until 60 months.

- Recurrent disease

This term is applicable during follow-up, to all patients that were not defined as treatment failures at 12 months. Recurrent disease is defined as flat (Paris type 0-IIb) USLs with MGIN or HGIN in biopsies from TA during FU, independent of baseline pathology. Recurrent disease will be treated with RFA initially, or escape treatment if persistent, as described in section 9.4.3

10. Risks and Benefits

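### Scenario #1 in Protocol 9.4.1 sends any MGIN+ biopsy from a normally stained treatment area to repeat RFA without excepting ESCC, against the synopsis, 9.4.3 and 9.10

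*Protocol*

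**What the plan says.** Protocol 9.4.1 directs treatment-phase visits by what Lugol's staining shows. In Scenario #1 (no unstained lesion), the purpose of the month-3 visit's biopsies is given as: "biopsy sampling of TA will be performed to confirm absence of occult MGIN or worse". If "any biopsy subsequently shows MGIN+ despite a normally stained esophagus, the entire TA is treated once again with circumferential or focal RFA". That is the only instruction in Scenario #1 for a positive result.

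Three other places in the current protocol deal with ESCC found on biopsy, and none depends on staining:

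- The Synopsis (Study Procedures and Assessments) sends patients with ESCC in biopsies during follow-up to escape treatment.
- Section 9.4.3 lists among its indications "ESCC in biopsies during treatment or follow-up phase (defined as progression of disease".
- Section 9.10 states "Progressive disease is defined as ESCC in any biopsy or resection specimen" and then "Progressive disease on biopsy will always be treated with escape treatment".

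**The concern.** A site that holds an ESCC report from a normally stained TA at month 3 finds two instructions. The scenario it is working in prescribes repeat RFA of the whole TA; the general rules prescribe escape treatment. The subject has histological cancer, so the protocol should not leave the site to work out which text prevails. There is also a smaller effect on the data. The route taken decides whether the subject is recorded under additional RFA (SAP 7.7) or falls in the escape-treatment subgroup (Protocol 13.6).

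**Working it through.** No arithmetic applies. The check sets the passages side by side.

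**Step 1. Does MGIN+ reach ESCC?** The term is missing from the glossary and from 9.10. Four things bear on its meaning:

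- Scenario #1 takes its biopsies to look for MGIN or worse, so MGIN+ reads as shorthand for that.
- Protocol 6.2 describes an earlier study that treated until MGIN or worse was eradicated, with complete response "defined as the histological absence of MGIN, HGIN, or ESCC". There the term includes ESCC.
- The pathology scale in 9.1.1 places invasive carcinoma (category 6) above MGIN (4) and HGIN (5).
- The other use of the shorthand, in the discharge instructions under 9.4.3 ("no further MGIN+ and no need for further RFA"), sets no upper limit.

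Nothing stops MGIN+ at HGIN. That it includes ESCC is an inference, but a strong one.

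**Step 2. How do the other branches treat ESCC?**

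| Place in Protocol | MGIN or HGIN on biopsy | ESCC on biopsy |
|---|---|---|
| 9.4.1 Scenario #1 (normal staining) | Repeat RFA of the entire TA | No separate sentence; falls under MGIN+ |
| 9.4.1 Scenario #2 (flat unstained lesions) | RFA | Separate sentence: progressor, primary-endpoint failure, escape treatment offered |
| 9.4.2 items iv.2 and iv.3 (follow-up phase) | RFA at 3-month intervals, grades named | Separate item: escape treatment |
| 9.4.3 and 9.10 | – | Escape treatment |

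Scenario #3 does not clearly fill the gap. Its trigger for an earlier ESCC biopsy is tied to a particular lesion, and in Scenario #1 no lesion is visible.

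**Step 3. When can the conflict arise?** Under Scenario #1 a normally stained TA is biopsied at month 3 but not at months 6 or 9, and no RFA is given at month 12. The exposure is therefore essentially the month-3 mapping biopsy.

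**Step 4. Does any endpoint change?**

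- Primary endpoint: Protocol 5.2.1 and SAP 7.9.1 make ESCC in a biopsy a failure even if month-12 biopsies show CR, and 9.10 agrees. Scenario #3 words failure in terms of escape-treatment histology, but it is written for visible suspicious lesions and does not govern here.
- Secondary endpoint 3 (Protocol 5.2.2, SAP 7.9.2) counts ESCC in the TA in biopsy or resection specimens within the first 12 months, so the subject is included whichever instruction is followed.
- Secondary endpoint 7 is restricted to patients with CR at 12 months, so this subject does not enter it.

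**The case against.** The strongest reply is that the intent is readable. The synopsis, 9.4.3 and 9.10 all give one general rule for ESCC, 9.10 with the word always, and Scenario #2 shows the drafting pattern that Scenario #1 probably omitted by oversight. Safeguards exist as well. Post-RFA biopsies are read at the lead site and specimens of progressive disease by two pathologists (9.1.1), a CICAMS expert observes each treatment-phase endoscopy (9.4.1), and 9.4.3 allows escape treatment on clinical indication. Protocol 9.1 also says that Figure 1 sets out every decision point; the figure is not shown and may separate ESCC. All of this stands. It makes the fault a missing exception rather than two deliberately opposed rules, and it means one cannot say that a site would in fact follow Scenario #1 for cancer. It does not remove the contradiction from the text.

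Three stronger readings are tempting, and the documents do not support them:

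- **A rate.** A reader might take from Protocol 6.2 that the event has happened and put it at 2/78 = 2.6%, since "Two progressor lesions were normally stained after Lugol's and with repeatedly negative biopsies, and were therefore left untreated". Those lesions had negative biopsies, so the Scenario #1 rule would not have been triggered. They also belong to long-term follow-up, where 9.4.2 of the present protocol already separates ESCC. Pathology showed cancer in one and was pending for the other. The ratio is not a rate for ESCC in a month-3 mapping biopsy.
- **Distorted endpoints.** A reader might infer that endpoint counts are at risk. Step 4 of the working shows that they are not.
- **Lost pathology.** A reader might infer that repeat RFA forfeits a resection specimen that the other route guarantees. Escape treatment under 9.4.3 may be radiotherapy or chemotherapy, which yield none either, and under 9.10 the biopsy alone establishes progression.

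**Conclusion.** The contradiction is real and lies in the current protocol text. Read literally, ESCC in a month-3 biopsy from a normally stained TA meets both the Scenario #1 instruction and the instruction in the synopsis, 9.4.3 and 9.10. Its weight comes from the consequence for the individual subject. Its frequency cannot be estimated: the documents give no rate, the protocol calls any positive biopsy in this setting very unlikely, and the number of affected subjects may be zero. Primary-endpoint failure and membership of endpoint 3 are unaffected. The conclusion assumes that MGIN+ means MGIN or worse, and it concerns the text only, since Figure 1 could not be checked. The point is worth correcting because it concerns management of cancer and costs almost nothing; it is not a threat to the primary analysis.

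**What to change.** In the next amendment, reconcile Scenario #1 of Protocol 9.4.1 with the synopsis, 9.4.3 and 9.10. Name the histological grades that MGIN+ covers in that sentence, and state, or cross-reference, which instruction applies when the biopsy shows ESCC. Check that Figure 1 agrees. Which instruction applies is a clinical decision for the sponsor and investigators; this review takes no position on it. The endpoint definitions and the SAP need no change on this account. The cost is about one sentence in the protocol and a check of the figure.
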